The proposal submitted here to investigate rs2297480 within S0307 will build upon these findings and will investigate additional SNPs and pathways that may be predictive of response (efficacy and/or toxicity) to bisphosphonate therapy. This data may be applicable to patients receiving bisphosphonate therapy for breast cancer risk reduction but may also lend itself to the broader public health concern of osteoporosis and its therapies.

Primary Outcome to be assessed: Acute Phase Reactions: The nitrogen containing bisphosphonates are associated with acute phase reactions with the associated fever, chills, bone pain, myalgias and arthralgias and may occur with oral or intravenous bisphosphonate therapy. Fever has been reported in 9–44% of patients receiving intravenous nitrogen containing bisphosphonates. Typically occurring within 48 hours of infusion, fever is usually low-grade, though occasionally associated with rigors. Accompanying bone pain has also been reported in over half of the patients and the reactions typically are self-limited and resolve completely within 24-48 hours although patients may experience significant discomfort during this time. Most often the acute phase reaction occurs with the initial dosing of the intravenous nitrogen containing bisphosphonates and typically does not occur or is less severe with subsequent doses. Presently there is no mechanism to predict which patients may experience this toxicity.

In a clinical trial investigating bone health in postmenopausal women comparing orally administered nitrogen containing bisphosphonates (alendronate and ibandronate), the acute phase reaction symptoms were higher with ibandronate (6.8%) that with alendronate (3.0%) (Miller, Curr Med Res Op 2008). Of note, this study of postmenopausal women with osteoporosis used a lower dose of ibandronate (150 mg orally monthly) then S0307 uses (50mg orally daily). The frequency of acute phase reactions may vary with the different dosing regimens and the disease process being treated. Data investigating the ibandronate dosed at 50mg daily for metastatic bone disease suggests that the acute phase reaction occurs in 2% of patients while zoledronic acid dosed at 4mg intravenously is associated with 26-27% of patients experiencing an acute phase reaction (Devitt Ther Clin Risk Mang 2008). The differences between rates of acute phase reactions may be attributed to the different biochemical structure of each of the bisphosphonates. Of note, not all patients experience the acute phase reaction, suggesting the possibility that this outcome may related to a genetic variable such as variability within the binding pocket of FDPS.

Acute-Phase Reactions Reported Within 14 Days of the First and Second Infusion in Patients with Breast Cancer or Multiple Myeloma

	Zoledronic acid 4 mg			
Infusion	First	Second		
Patients treated, n	563	542		
Arthralgia, n (%)	18 (3.2)	10 (1.8)		
Bone pain, n (%)	85 (15.1)	55 (10.1)		
Fever, n (%)	65 (11.5)	24 (4.4)		
Myalgia, n (%)	16 (2.8)	20 (3.7)		

http://www.medscape.com/content/2003/00/46/23/462348/462348 tab.html

S0307 captures the adverse events (symptoms and grading of symptoms) associated with each of the three bisphosphonates, clodronate, ibandronate and zoledronic acid and provides the ideal study design to test the hypothesis that SNPS within FDPS correlate with toxicity.

Patients with significant toxicities are of interest to this pharmacogenomic study. However, it is possible that patients who had enrolled on S0307 earlier and experienced a significant acute phase reaction (or other adverse event or outcome) may not be available now to donate circulating leukocytes for DNA studies. To address this, consideration will be given to assessing paraffin embedded tissues from these individuals for analysis, should appropriate consents be in place and tissue be available from that individual. **S0307** includes collection of paraffin embedded tumor tissue and there is an evolving body of data demonstrating that many SNPs are concordant between germline DNA of leukocytes and that of somatic tumor tissue. A study ongoing at the University of Michigan (PI: [name]) is investigating concordance of FDPS, VEGF and other bisphosphonate related genes within circulating leukocytes and paraffin embedded tissues. Since cancers contain a variety of mutations, circulating leukocytes remain a standard tissue for germline assessments, unless study SNP concordance has been shown with somatic tissue.

The adverse events to be used within this proposed analysis include: fever, flu like syndrome, musculoskeletal pain (back, bone, joint, limb, muscle) and pain (other). These will be pooled as a conglomerate "acute phase reaction" and patient may have multiple symptoms such as fever and bone pain.

Reporting of these adverse events in \$0307, as of August 28, 2008, has demonstrated the following findings (collapsed over treatment assignment):

	Grade of adverse event				
Adverse Event	≤1	2	3	4	5
Fever	881	1	1	0	0
Flu like syndrome	881	2	0	0	0
Musculo Pain: Back	877	5	1	0	0
Musculo Pain: bone	846	20	17	0	0
Musculo Pain: joint	833	37	13	0	0
Musculo Pain: limb	877	5	1	0	0
Musculo Pain: muscle	871	6	6	0	0
Pain Other	880	2	1	0	0

Since a patient can have multiple toxicities we computed the percentage having any of these toxicities. Twelve percent had a toxicity of Grade 2 or higher and 3% had a Grade 3 toxicity. These are limited to toxicities possibly, probably, or definitely related to bisphosphonate treatment.

Study Target Genes: The study genes (and SNPs) have been identified from the literature and through Cancer Genome Anatomy Project, HapMap and National Center for Biotechnology Information. The lead study SNP FDPS rs2297480 and the lead outcome measures are outlined here.

Genotyping Analysis for specific SNP assessment: The DNA will be extracted from circulating leukocytes at the SWOG Solid Tumor Tissue Bank in Colorado. An aliquot of DNA will be sent to the [name] laboratory at the University of Michigan for genetic analysis as outlined here. The SNPs to be investigated will be detected using Taqman® Allelic Discrimination Assay (Foster City, CA). DNA samples will be assayed for SNPs in our candidate genes. Briefly, a 2ul DNA sample will be added to a 25ul reaction containing forward and reverse primers along with 2 allele specific labeled probes (one wild-type and one variant allele specific). The PCR and fluorescence measurements will be performed using the ABI Prism 7700 sequence detection system. Since the genotyping field is rapidly evolving, the best approach available will be employed, and this may change over time. If a polymorphisms cannot be reliably genotyped using the Taqman Allelic Discrimination, then an alternative method(s) such allele specific PCR and restriction fragment length polymorphisms PCR (RFLP-PCR will be used.

Circulating Leukocytes: As per published methods ([name] 2003) (Miller 1988) the buffy coat will be created from the whole blood collected and DNA will be extracted using Qiagen DNeasy Tissue kit and the QIAamp DNA Blood Midi kit (Quiagen Inc, Valencia CA) according to manufacturer's instructions. The DNA yield will be assessed by spectrophotometery (Beckman DU 640, Beckman Coulter, Fullerton CA).

Management of the specimens and study assays are to be performed by leaders in the pharmacogenomic translational science field.

The research team has experience with pharmacogenomics within Intergroups and COBRA. Data generated through SWOG and Gynocologic Oncology Group related pharmacogenomic research performed by [name] (Kuptsova Blood 2007) (Krivak JCO 2008) and [name] through the NIH Pharmacogenetic Research Network (PGRN) and the Consortium on Breast Cancer Pharmacogentics (COBRA) (Jin JCO 2008) has demonstrated the viability of patient directed therapies and of individualized medicine. The PI of this proposed amendment ([name]) has experience investigating biomarkers in breast cancer and bone including study of correlation between breast tumor estrogen receptor status and bone mineral density (BMD), effect of breast cancer therapy on BMD and markers of bone metabolism, toxicities of bisphosphonates (renal and osteonecrosis of the jaw), genes associated with site specific metastases in preclinical studies, and biomarkers associated with taxane sensitivity. [name] is presently conducting a clinical study investigating concordance of FDPS and VEFG genes across a variety of tissues. Drs [name] and [name] are lead investigators of SWOG **S0702**, "A Prospective Observational Multicenter Cohort Study to Assess the Incidence of Osteonecrosis of the Jaw (ONJ) in Cancer Patients with Bone Metastases Starting Zoledronic Acid Treatment." S0702 banks serum and DNA for study of the effects of bisphosphonate therapy on the risk of ONJ. It is likely that the pharmacogenomic generated within S0307 and S0702 will complement each other and permit genomic validation of biologically important pathways.

Statistical Plan:

This translational study seeks to collect circulating leukocytes from as many, if not all patients, enrolled on \$0307 to build a well annotated DNA bank for present and future investigations relating to bisphosphonate therapy and cancer outcomes, as well as other potential pharmacogenomic questions. As of May 1 there were 3,425 of the 4,500 patients accrued to \$0307, with an accrual rate of approximately 293 patients within the last month. If 60-70% of enrolled patients donate DNA, then approximately 3000 patients will participate in this amendment, with an estimated 1000 patients per bisphosphonate arm (clodronate, ibandronate, zoledronic acid). There is some possibility that the accrual goal will be increased back to the original goal of 6,000 patients since the rapid accrual is shortening the overall follow-up period and therefore fewer events would be observed. That proposed amendment is currently under review by CTEP.

The power to investigate SNP FDPS rs2297480 and acute phase reactions within S0307 is outlined below. The specific sample size required for each SNP investigation is not presented here, as the study SNPs may evolve over time.

Primary Objective:

To investigate whether there is an association between inherited germ-line SNP FDPS rs2297480 and acute phase reactions in patients with early stage breast cancer who have been randomly assigned to one of three adjuvant bisphosphonates on clinical trial SWOG 0307.

FDPS SNP rs number	Allele Frequency
rs2297480	A:0.692; C: 0.308

We assume that the overall rate of an acute phase reaction Grade 2 or higher for the entire class of bisphosphonates is 12% based on the current data. We would like to detect a 5% absolute difference in acute phase reactions due to SNP effects. The 5% is large enough to be a clinically meaningful difference. To detect such a difference with 90% power (2-sided α = 0.05) we would need 2,272 samples. That is, the minor allele (C) would have a toxicity rate of 15.4% and the major allele (A) a rate of 10.4% (5% difference; 12% overall rate). If we are able to obtain the expected 3,000 patients, then the power increases to 96%. That sample size would allow us to detect a 4.4 % difference or larger between the minor and major alleles with 90% power. The analysis would use logistic regression on the outcome (acute phase reaction) by allele type stratified by treatment type. Additive, dominant, and recessive models will be considered for the three genotypes as well. The additive model uses (0,1,2) coding for AA, AC, and CC, respectively. The dominant model uses coding (0,1,1) and the recessive model (0,0,1).

Secondary Objectives:

The proposed amendment will investigate whether the study SNP FPDS rs2297480 and acute phase reactions associate together specifically in the setting of one bisphosphonate or the nitrogen containing bisphosphonates or appears generic to the class of drugs.

If we wish to detect a difference in acute phase reactions within each drug (n=1000), then with 90% power using a 2-sided α = 0.05, we could detect a 7.8% difference (17.4% versus 9.6%) between the minor and major alleles. To demonstrate that the acute phase reaction rate depends on which drug, we would look for an interaction between treatment and allele type. Suppose that one treatment shows no effect of allele type (12% for both major and minor alleles), but that the other treatment shows a 10.2% difference (19.1% versus 8.9%), then we would have 90% power to detect that interaction. The analysis would use logistic regression on the outcome (acute phase reaction) by allele type, treatment type, and their interaction.

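### The SNP-by-drug interaction example in Appendix 19.3 is stated to have 90% power; on its own inputs the planned logistic interaction test has about 86-87%

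*Combined protocol and SAP*

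**What the plan says.** The first secondary objective of Appendix 19.3 asks whether the association between the FDPS SNP and acute phase reactions is specific to one bisphosphonate, to the nitrogen-containing ones, or common to the class. The Statistical Plan addresses this in one paragraph under Secondary Objectives.

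- It first considers each drug alone, with 1,000 women and "with 90% power using a 2-sided α = 0.05", and gives a detectable allele difference of 7.8 points (17.4% versus 9.6%). The 1,000 comes from the opening of the Statistical Plan, which expects about 3,000 DNA donors, "with an estimated 1000 patients per bisphosphonate arm".
- It then turns to the interaction: "Suppose that one treatment shows no effect of allele type (12% for both major and minor alleles"), while "the other treatment shows a 10.2% difference (19.1% versus 8.9"), and states "then we would have 90% power to detect that interaction".
- The test is named: "The analysis would use logistic regression on the outcome (acute phase reaction) by allele type, treatment type, and their interaction".

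The allele frequencies for rs2297480 are given under the primary objective as "A:0.692; C: 0.308". No power formula is printed for the interaction example.

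**The concern.** The example sets the rates in all four allele-by-drug cells, so its power can be computed directly. Two of the cells are not at 12%. The cell at 19.1% is one of the two smaller ones (308 women), and on the risk-difference scale it contributes the largest share of the variance. A calculation that treats every cell as if it were at 12% understates the standard error on that scale and so overstates power.

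This sentence is the only power the plan gives for the formal interaction test. A reader who later meets a non-significant interaction would use it to judge how much the null result excludes. The background in Appendix 19.3 does not expect an FDPS association for clodronate, so a difference between drugs is a question of real interest.

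**Working it through.** **Inputs, all from Appendix 19.3, Statistical Plan**

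- 1,000 women per drug, two drugs compared, two-sided alpha 0.05. The alpha is stated for the within-drug calculation just before and is carried over here.
- Allele split 0.308/0.692, so 308 (C) and 692 (A) per drug. The printed rates fit this split: 0.308 × 19.1% + 0.692 × 8.9% = 12.0%.
- Rates: drug 1, 12% and 12%; drug 2, 19.1% (C) and 8.9% (A).

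The 12% overall rate and the counting of one allele per woman are taken as the plan states them.

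**Step 1. Reproduce the printed 90%.** Use the difference between the two risk differences and give every cell the variance of a 12% rate:

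- SE = √[2 × 0.12 × 0.88 × (1/308 + 1/692)] = √0.000991 = 0.03148
- z = 0.102 / 0.03148 = 3.24; power = Φ(3.24 − 1.96) = 90.0%
- Detectable difference at 90% power = (1.960 + 1.282) × 0.03148 = 0.1020, that is 19.06% versus 8.86%

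This returns the printed 10.2 points, 19.1% and 8.9%.

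**Step 2. Use each cell's own rate, logistic scale (the planned test).**

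- Log odds ratio in drug 2: logit(0.191) − logit(0.089) = −1.4435 + 2.3259 = 0.882; in drug 1 it is 0.
- Variance = Σ 1/[n p (1−p)]:

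| Cell | n | p | 1/[n p (1−p)] |
|---|---|---|---|
| Drug 1, C | 308 | 0.120 | 0.03075 |
| Drug 1, A | 692 | 0.120 | 0.01368 |
| Drug 2, C | 308 | 0.191 | 0.02101 |
| Drug 2, A | 692 | 0.089 | 0.01782 |
| Sum | | | 0.08327 |

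- SE = √0.08327 = 0.2886; z = 0.882/0.2886 = 3.06; power = Φ(3.06 − 1.96) = **86.4%**

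**Step 3. Same rates, risk-difference scale.** The variances p(1−p)/n are 0.000343, 0.000153, 0.000502 and 0.000117; they sum to 0.001114, so SE = 0.03338. Then z = 0.102/0.03338 = 3.06 and power = **86.3%**.

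**Step 4. Simulation of the planned test.** With 200,000 simulated trials, power is 87.0% (Wald), 87.2% (likelihood ratio) and 87.1% (score).

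**Step 5. What 90% would need.** At 1,000 per drug, with the overall rate held at 12%, the logit Wald formula needs a difference of 10.8 points (19.5% versus 8.7%). At the printed rates it needs about 1,124 women per drug.

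**Sensitivity to rounding.** Moving the printed rates within their rounding changes the corrected power only between about 85.7% and 87.1%.

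**The case against.** **Other approximations come closer to 90%.** A hybrid on the risk-difference scale, with the critical value from the null variance and the spread from the alternative, gives 88.6%. It is not the logistic test that the plan names, it would give a detectable difference of 10.45 points instead of 10.2, and it is still below 90%. A two-degree-of-freedom test across all three drugs gives 90.2% on the logit scale if one drug carries the effect, and 88.8% if two do. But the example contrasts one treatment with the other, which describes two drugs.

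**The sample size may turn out larger.** The 1,000 per arm was estimated while the accrual goal was 4,500. Section 11.2 now targets 2,000 each for zoledronic acid and clodronate. At the appendix's 60-70% donation rate that is 1,200 to 1,400 donors in each of those arms, and the formula in step 2 then gives about 92% to 95% power. This stands as a remark on the zoledronic acid versus clodronate contrast, and applies less to contrasts with ibandronate (target 1,400). It does not make the printed sentence correct at its stated 1,000 per drug.

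**The cause is not documented.** A reader might infer that the plan is shown to have used the null variance. The documents do not support stating that as fact, because no formula is printed. The exact match in step 1 is strong evidence, but other figures in the appendix come from another method: the 2,272 samples for the primary SNP question reproduce with a two-proportion formula using the alternative rates and a continuity correction. The shortfall does not depend on the cause.

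**The drug-specificity question has other support.** A reader might also infer that this is the only power information on whether the effect is specific to a drug. The same paragraph gives the within-drug detectable difference of 7.8 points, which checks at 89.4% power (unpooled) to 92.1% (null critical value, alternative spread). The example is the only power for the formal interaction test, and the point goes no further than that.

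**Conclusion.** The stated 90% is about 3 to 4 points too high. On the example's own inputs the planned logistic interaction test has about 86-87% power for a 10.2-point difference at 1,000 women per drug; 90% power needs about 10.8 points. The result rests on the two-drug reading, the 308/692 split, two-sided alpha 0.05 and the printed cell rates.

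The consequence is small. The example is illustrative, belongs to a secondary objective of an optional translational study, and sets no sample size, test or decision rule. The disease-free survival design, the interim boundaries and the 2,272-sample calculation for the primary SNP objective are unaffected.

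**What to change.** In Appendix 19.3, Statistical Plan, Secondary Objectives, restate the interaction example in one of two ways, computed from the actual cell rates:

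- about 86-87% power for a 10.2-point difference (19.1% versus 8.9%) at 1,000 per drug; or
- 90% power for a difference of about 10.8 points (19.5% versus 8.7%) at 1,000 per drug.

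State the method used (for example, a Wald test of the logistic interaction) and keep the sample size per drug in the sentence, so that the figure can be updated when the number of DNA donors is known. The cost is one sentence; no change to design, data collection or analysis is needed.

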We will compare all three agents simultaneously to determine if there is a significant difference among the three agents (called the omnibus or global test). If the omnibus test shows a significant overall effect at level α , then we will proceed with three pairwise comparisons, each at level α (Liu and Dahlberg, 1995). This conditional sequence is more powerful than using a Bonferroni procedure testing each pairwise comparison at $\alpha/3$ without the preliminary overall test. Alpha is determined by the timing of the analysis (e.g. interim analysis or final).

Endpoints

The primary endpoint is invasive disease-free survival (DFS). This is the time from registration (randomization) to death by any cause, local, regional or distant recurrence, or a new breast primary whichever comes first. In situ disease is not counted as a recurrence. Patients not having an event are censored at the last follow-up visit. The primary secondary outcomes are overall survival and toxicity. Overall survival is time from registration to death by any cause. Site of first metastases is a secondary endpoint of interest since bisphosphonates should prevent metastases to bone.

Stratification

Due to the large sample size, randomization was not stratified by any prognostic factors. Time of randomization will be a stratifying variable in the analysis as described below.

Interim analysis

Interim analysis begins when approximately 31% of the expected failures are recorded. This should occur early in 2011. Annual interim analyses are performed thereafter. Decision making following a significant interim analysis is described in the protocol.

Year	Analysis	Percent of Events	Alpha Level for Test	Cumulative probability
4	Interim 1	31%	0.0010	0.0010
5	Interim 2	46%	0.0012	0.0022
6	Interim 3	60%	0.0068	0.0077
7	Interim 4	74%	.0158	0.0158
8	Interim 5	87%	.0265	0.0265
9	Final	100%	.0391	0.0500

Accrual goal

This trial has a complex history with regard to the accrual goal. The trial was designed to include 6,000 patients with 2,000 per arm. Accrual was expected to be 125 per month. After the trial was activated, accrual was very slow. This was possibly due to reports of osteonecrosis associated with bisphosphonates, particularly zoledronic acid. After one year, NCI clinical trial guidelines require amendment of the sample size goals such that projected monthly accrual is consistent with actual accrual. The trial was amended to accrue 62.5 patients per month, consistent with the observed accrual at that time. The

[figure not shown]

sample size goal was lowered to 4,500 based on the slower accrual and hence longer median follow-up time. The same effect sizes were used so only accrual and follow-up time considerations were changed. After the change in sample size goals, the pharmaceutical manufacturer of ibandronate revised the contract to provide support for a total of 1,500 patients instead of 2,000. The other two contracts remained at 2,000 patients.

Immediately after the amendment to change the accrual goal, accrual picked up dramatically. It was further accelerated by a report at ASCO in June 2008 of the benefit of zoledronic acid found in another trial (ABCSG-12). By early 2009 accrual had reached 300 patients per month. It became clear that the accrual goal of 4,500 patients would be met two years early and thus median follow-up time would be too short. We submitted a new amendment to increase the total accrual goal to 5,400 patients. This would restore the accrual goal to 2,000 per arm for zoledronic acid and clodronate, but limit accrual to only 1,400 patients for ibandronate. Ibandronate was no longer going to be marketed in the U.S. market for this indication and the manufacturer did not want to increase its level of support. The amendment was approved July 23, 2009.

At the end of July 2009, SWOG announced that the trial would close temporarily on August 24, 2009 due to a change in design. The change in accrual would require a change in the random allocation to treatment since the informed consent specified equal allocation to the three arms and thus any change in random allocation would require a revised informed consent. It was necessary to close the trial so that sites could update their IRB approval before they would be allowed to open the trial again. The pending closure sparked increased demand such that 488 patients were registered in a 3-week period corresponding to a rate of 600/month. By the time the trial closed temporarily on 8/24/09 there were 4,747 patients with 1,567 allocated to ibandronate. This exceeded the goal in this arm by 167 patients. The trial was designated to re-open on September 1, 2009 with only two arms since the ibandronate arm was complete. All institutions had to renew IRB approval before being allowed to register patients again. Accrual has started to reach its former levels, reaching 256 patients in December 2009. In order to obtain 2,000 patients in the two remaining arms, the total accrual will be approximately 5,600 since the ibandronate arm was overaccrued. At the current rate this should occur very early in 2010. Accrual to the trial will close on February 1, 2010. The change in the randomization allocation has an impact on the analysis plan as described below.

Power

While the accrual rates and total accrual goals have changed, the underlying expected effect sizes have been held constant for the duration of the trial. It was assumed that all pairwise comparisons were of equal interest and would be 2-sided. For the purpose of power calculations, clodronate was assumed to have the lowest expected DFS of 80% at five years. The best treatment was expected to have a 5-year DFS of approximately 83.4% or a hazard ratio of 1.25 for clodronate versus the best treatment. The intermediate treatment would have a HR between 1.25 to 1.00 when clodronate is compared to it. Power is a function of the actual location of this intermediate treatment and ranges from 78% to 93% for the omnibus test for the 5,400 sample size. Power is the lowest if the intermediate treatment is exactly in the middle of the two extremes and highest when the intermediate treatment is closer to one of the extremes. Power for the pairwise comparison of clodronate versus zoledronic acid ranges from 85% to 89% if HR=1.25. Power for ibandronate versus the other two agents individually is 77-85% for a HR=1.25 due to the smaller sample size. Power for the pairwise comparisons includes conditioning on a significant overall omnibus test. Power calculations were also computed for the Bonferroni approach which showed lower power than the chosen approach.

When the accrual goals and rates were changed officially, power in the range 80%-90% was maintained in most likely scenarios by changing the accrual goal to fit the actual expected accrual rate. In the last revision of the accrual goal, the change in accrual by month was incorporated into the power calculations (i.e. uniform accrual was not assumed). Actual outcome rates in the trial were never used to make changes in the accrual goals. Power was always based on the same effect treatment effects as used in the initial trial design.

Analysis

The primary analysis of DFS is a comparison of all three groups using a log-rank test performed at level α . If significant, this would be followed by three pairwise comparisons also performed at level α . The change in randomization probabilities must be considered as well since it could affect the results if not accommodated in the analysis. Suppose that over the course of the trial that overall DFS actually increased due to better adjuvant treatment, but that the hazard ratios linking the three groups were fixed over the duration of the study. Assuming that the treatment hazard ratios are constant over the study duration is the usual assumption in any randomized trial. However, there could still be "temporal drift" in absolute survival over time that affects all three groups equally. This drift poses no problem for the analysis if the randomization allocation does not change over time since all three groups are affected in the same way. However, in this case the allocation probabilities were changed since the ibandronate group was closed in August 2009. This change needs to be accommodated in the analysis. Even if the ibandronate group was not closed, but had a highly reduced allocation probability (e.g. from 33.3% to 1%) that change must be considered in the analysis as shown below.

Let s=1, 2 where s=1 is the period of equal randomization to three groups (up to 8/09) and s=2 is the period of changed allocation. In this study it is randomization to the two groups in equal allocation from 9/09 on. However, it could be any dramatic change in randomization (e.g. metering ibandronate to 1% so that there is still randomization to three groups over the course of the trial). Our underlying model for the hazard rate is the following:

$$\lambda_{s}(t;trt) = \lambda_{0s}(t) e^{\beta_{1} \text{ zoledronic} + \beta_{2} \text{ ibandronate}}$$
(1)

where $\lambda_{0s}(t)$ is the baseline hazard rate for clodronate in randomization period 1 or 2. The baseline hazard rates for the two periods need not be the same since temporal drift may have occurred. Because of the stratification, patients are compared only within their own stratum, i.e. during the same contemporaneous randomization period. In stratum 2, there are no patients randomized to ibandronate so there is no contribution to the estimate of β_2 in that period. We do assume that the hazard ratio of zoledronic acid to clodronate is the same in both periods. This can be seen in the more general model:

$$\lambda_{s}(t;trt) = \lambda_{0s}(t) e^{\beta_{1} zoledronic + \beta_{2} ibandronate + \beta_{3}(s-1)* zoledronic}$$
 (2)

where β_3 would represent a change in the HR between zoledronic acid and clodronate from the first randomization period to the next. In fact, the estimates β_1 and β_2 in model (2) exactly correspond mathematically to what would be obtained by excluding all patients randomized after the change in randomization to two arms. Therefore, model (2) is very inefficient since it assumes a change in HR. Model (1) represents the usual assumptions in randomized trials about constant treatment hazard ratios during the conduct of the trial, but allows the baseline hazard to change by randomization period. Furthermore, contemporaneous randomization is retained since patients are compared only within their own stratum.

The omnibus test corresponds to a joint test of $\beta_1=\beta_2=0$ from Model (1). The stratified log-rank test is the score test corresponding to the test of this hypothesis. If that test is significant, than we proceed with pairwise comparisons. For the pairwise comparisons, only the comparison of zoledronic acid to clodronate is based on both randomization periods. Essentially, it is the test of $\beta_1=0$ from Model (1). The pairwise comparisons of ibandronate to (1) clodronate and (2) zoledronic acid will be based only on period 1. These tests are mathematically equivalent to testing (1) $\beta_2=0$ and (2)

 $(\beta_2 - \beta_1) = 0$ in Model (2). There is a slight loss of power in the pairwise comparisons involving ibandronate since only data from the first time period are used. Thus, all pairwise comparisons are performed in contemporaneous periods, while the omnibus test is based on the stratified model (1).

In the absence of temporal drift, stratification is not strictly necessary, but accounting for it causes little loss in power. If there is temporal drift, then failure to account for it could lead to bias when changing allocation probabilities. Simulation for extreme drift in DFS over time shows that alpha is inflated to 7% under the null hypothesis when stratification is not used. Even if the third group is "metered" (randomization for ibandronate continues at a low level), there is still inflation of alpha in the presence of temporal drift. This is due to imbalance in projected outcomes since patients have different projections over time. Thus, any change in randomization allocation must be addressed in the analysis. Our simulation shows that alpha is correctly maintained by stratification in the presence of temporal drift.

With regard to power, maximal power is obtained using stratified model (1) above for the omnibus test. Power is 85% to 92% depending on the distribution of the three groups. Pairwise comparisons range in power from 83% to 90% for the two extreme groups. These estimates are based on an expected final sample size of 5,600.

Therefore, the primary analysis will be based on Model (1) to obtain the significance of the overall comparison and the pairwise comparison of zoledronic acid to clodronate. The two remaining pairwise comparisons (ibandronate vs. clodronate and ibandronate vs. zoledronic acid) are based on the first time period only when there was randomization to ibandronate.

Secondary comparisons will include adjustment for prognostic factors such as HER2 status, AJCC stage, and hormone-receptor status. Subgroup analysis will include determination of the hazard ratios (compared to clodronate) separately by age group, race, Her2 status, hormone-receptor status, AJCC stage, and type of adjuvant treatment received. These will be presented in a forest plot so that apparent discrepancies from the overall results will be visually apparent. These latter analyses are exploratory as there are no expected interactions of treatment with these prognostic factors.

Reference

